DOC, defined as 2^{0/7} gestational weeks, will be calculated as first day of LMP plus 14 days (2 weeks).

If EDD is not reported by the HCP but LMP data are available, the registry will use first day of LMP to calculate EDD, gestational age, and DOC.

Individuals will be considered exposed during pregnancy if the exposure occurs any time from 25 days prior to the DOC to the pregnancy outcome. For the analysis of MCM, first trimester exposure will be defined as exposure from 5 times the product's half-life (i.e., 25 days for tirzepatide) prior to the DOC to 13^{6/7} gestational weeks.

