9.9. Study Size

9.9.1. Sample Size

Table 9.4 presents by outcome the sample size (number of live births or pregnant individuals, depending on the outcome) required in each cohort to detect a range of relative risks, from 1.5 to 5.5. Sample size calculations were performed with SAS® statistical software (version 9.4 or higher, SAS Institute, Cary, NC) for the outcomes using the Fisher's exact conditional test with Walters normal approximation method, and assuming a power of 80%, a 2-sided α level of 0.05, an equal number of individuals in each cohort (although other sampling ratios were considered), and observed prevalence of the outcomes in the comparator cohort equivalent to reference rates in the general population. These general population rates were obtained for most (but not all) of the outcomes from various sources, including the Metropolitan Atlanta Congenital Defects Program (MACDP), the National Vital Statistics System (NVSS), and published literature.

Although the registry aims to examine a variety of maternal, fetal, and infant outcomes, the target sample size for the registry is based on the primary outcome, overall prevalence of MCM, which also is the outcome with the most restrictive denominators and one of the lowest prevalence in the general population.

As shown in Table 9.4, 265 live births in the analysis population of each cohort are needed to detect a 3-fold increase in the overall prevalence of MCM between cohorts, or a relative risk of 3.

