total of 1,092 individuals would need to be enrolled in the registry. This sample size will afford the study the ability to detect a 3-fold increase in the overall prevalence of the primary outcome, MCM, in the tirzepatide-exposed cohort, with meaningful confidence (95% confidence level). Additionally, [Table 9.5](#) shows that, without any adjustments for multiple comparisons, the proposed sample size will also afford the study >80% power to detect a 3-fold increase in several of the secondary and exploratory outcomes.

The overall prevalence of MCM is higher among individuals with obesity (BMI >30 kg/m²; 3.9%²⁶) than that of the general population (3%).⁷⁴ However, because it is difficult to estimate the proportion of enrolled individuals who will have obesity at the time of conception (as some will have lost weight prior to conception due to weight management treatment), the more conservative approach assuming an overall prevalence of 3% has been chosen (i.e., the overall sample size calculations were based on the general population prevalence of MCM). Had the higher rate (3.9%) been used, the total sample size for the registry would have been substantially lower (828 vs. 1092). These assumptions also may be re-evaluated after interim analyses have been conducted.

Table 9.4. Sample Size Needed per Cohort to Detect Specific Relative Risk (Exposed: Tirzepatide Unexposed^c)

Outcomes ^a	Reference Prevalence in Unexposed Group	Reference	Denominator of Reference	RR= 1.5	RR= 2.0	RR= 2.5	RR= 3.0	RR= 3.5	RR= 4.0	RR= 4.5	RR= 5.0	RR= 5.5
Primary Objective												
MCM	3.0%	CDC 2008 ⁷⁴	Live births	2,627	796	413	265	190	146	117	97	82
Secondary Objectives												
Pre-eclampsia	3.8%	Ananth 2013 ⁷⁵	Pregnant individuals	2054	622	322	206	148	113	91	75	64
Eclampsia	0.281%	Butwick 2020 ⁷⁶	Live births	28973	8824	4600	2961	2130	1640	1322	1101	940
Gestational diabetes	6.9%	Martin 2021 ⁷⁷	Pregnant individuals	1161	350	180	115	82	62	50	41	35
Pregnancy-induced hypertension	6.5%	Butwick 2020 ⁷⁶	Pregnant individuals	1088	327	169	107	76	58	46	38	32
SAB	11.8%	Wu 2019 ⁷⁸	Pregnant individuals	596	177	90	57	40	30	24	19	16
Stillbirth	0.596%	MacDorman 2015 ⁷⁹	Live births and stillbirths	13610	4142	2159	1389	999	769	619	516	440
Induced abortion	18.6%	Jatlaoui 2019 ⁸⁰	Live births	343	100	50	31	21	15	12	9	NA ^b
Preterm birth	8.47%	Martin 2021 ⁷⁷	Singleton live births	868	260	134	85	60	46	36	30	25
SGA	10.0%	By definition	Live births	721	215	110	70	49	37	29	24	20

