9.11.2. Statistical Methods

Registry data will be summarized in tables and listings by study cohort, as appropriate. These data include maternal demographic characteristics and pre-pregnancy anthropometrics, pregnancy information, maternal obstetrical history, family history of congenital malformations, disease information, maternal exposures during pregnancy, pregnancy outcome information (including gestational age of outcome), and infant outcome information.

For each continuous variable, the number of observations, median, mean, standard deviation, minimum, and maximum will be reported. For each categorical variable, the frequency and percentage in each category will be reported. The frequency and percentage of participants with missing data for each data point will be presented. Results will be rounded to one decimal place; therefore, percentages may not always add up to 100.

Pair-wise comparisons of demographic and baseline characteristics and event rates of the outcomes of interest will be conducted between the study cohorts, as follows:

- Comparison #1: Tirzepatide exposed cohort vs. AOM active comparator cohort

- Comparison #2: Tirzepatide exposed cohort* vs. AOM unexposed comparator cohort
*Comparison #2 will include a subset of tirzepatide exposed cohort who have obesity or are overweight with at least one weight-related comorbid condition at the time of conception so as to improve comparability to AOM unexposed comparator cohort with the same obesity-related eligibility criteria.

For the analysis, participants from all countries will be pooled. Comparisons will be conducted using the methods described below, and p-values and 95% confidence intervals will be reported, as appropriate, to reflect statistical uncertainty. All outcomes will be analyzed as binary variables. The study is not powered for multiple comparisons; thus, p-values associated with secondary or exploratory outcomes will be nominal.

In addition, the prevalence of the outcomes in the general population and/or populations of individuals overweight or with obesity, from the literature, will be used to put the registry-observed outcome prevalences into context.

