9.11.2.2. Analysis of Secondary and Exploratory Outcomes

Prevalence of the secondary and exploratory outcomes will be calculated according to the conventions described in [Table 9.7](#). In general, the prevalence of each outcome will be calculated by dividing the number of cases of the outcome by the appropriate denominator for that particular outcome, based on clinical knowledge.

Table 9.7. Calculation of Secondary and Exploratory Outcome Prevalence

Outcome [Exposure window]	Numerator	Denominator
Secondary outcomes		
Maternal pregnancy complications		
Gestational diabetes [Exposure: Any trimester]	Individuals with gestational diabetes	Individuals included in the analysis population
Sensitivity analysis: Gestational diabetes	Gestational diabetes among pregnancies with pregnancy outcome data	Individuals with pregnancy outcome data
Pregnancy-induced hypertension [Exposure: Any trimester]	Individuals with pregnancy-induced hypertension	Individuals with pregnancy of 20 gestational weeks or more
Sensitivity analysis: Pregnancy-induced hypertension	Pregnancy-induced hypertension among pregnancies with pregnancy outcome data	Individuals with pregnancy of 20 gestational weeks or more with pregnancy outcome data
Pre-eclampsia [Exposure: Any trimester]	Individuals with pre-eclampsia	Individuals with pregnancy of 20 gestational weeks or more
Sensitivity analysis: Pre-eclampsia	Pre-eclampsia among individuals with pregnancy outcome data	Individuals with pregnancy of 20 gestational weeks or more and with pregnancy outcome data
Eclampsia [Exposure: Any trimester]	Individuals with eclampsia	Individuals with pregnancy of 20 gestational weeks or more
Sensitivity analysis: Eclampsia	Eclampsia among individuals with pregnancy outcome data	Individuals with pregnancy of 20 gestational weeks or more with pregnancy outcome data
Fetal Outcomes		
SAB [Exposure: DOC to $\leq 19^{6/7}$ gestational weeks]	SABs among individuals with pregnancy outcome data who are enrolled (and exposed, if applicable) prior to 20 gestational weeks	Individuals with pregnancy outcome data who are enrolled (and exposed, if applicable) prior to 20 gestational weeks
Induced abortion [Exposure: Any trimester]	Individuals with pregnancy ending in induced abortions	Individuals included in the analysis population
Sensitivity analysis: Induced abortion	Induced abortions among individuals with pregnancy outcome data	Individuals with pregnancy outcome data

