- For SAB and preterm birth, prevalence will be calculated among the subset of individuals who are enrolled in the registry prior to 20 and 37 gestational weeks, respectively. Additionally, for these time-to-event outcomes, data will be censored at appropriate time points: 20 gestational weeks for SAB and 37 gestational weeks for preterm birth.
- For pregnancy complications prevalence will be calculated according to the following assessment windows:
 - Pregnancy induced hypertension reported for the first time among participants after 20 weeks gestation.
 - Pre-eclampsia/eclampsia reported among participants after 20 weeks of gestation.
 - New-onset gestational diabetes reported among participants at any time during pregnancy
 - Inadequate maternal weight gain reported among participants at any time during pregnancy.
 - HG reported among participants anytime during pregnancy.
- Prevalence will be calculated at multiple time points for postnatal growth deficiency, rapid infant weight gain, and infant developmental delay will be assessed at 4 months (± 2 weeks) and 12 months (± 2 weeks) of infant age. At each time point, prevalence will be calculated among infants with data available for the particular outcome at that time point. If there is no assessment available at 4 and/or 12 months, available data will be evaluated based on the actual time of assessment (e.g., if the infant was measured at 6 months, these data will be compared to the values appropriate for a 6-month-old infant based on the growth charts). However, only development at 4 and 12 months will be reported as study outcomes, results from other time points will be reported in a separate category.

The unweighted univariate regression will be used to compare the crude (unadjusted) RRs for all outcomes. Adjusted methods will incorporate weights estimated using the IPTW method to balance the cohorts with regard to observable covariates (Section 9.11.2.4). A weighted generalized linear model using a binomial family and a log (relative risk) link will be employed to estimate an adjusted relative risk.

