9.13. Limitations of the Research Methods

Because this is an NIS, potential confounding factors cannot be ruled out. Data collection will reflect routine clinical practice rather than mandatory assessments at pre-specified time points, which may have an impact on the amount of data and its interpretation.

The general limitations of pregnancy registries with voluntary participation are well known, and these will apply to this study as well. One key limitation of the study is the limited size of the population of pregnant individuals expected to be exposed to tirzepatide for weight management during pregnancy.

Another key limitation of the registry, due to the voluntary nature of participation, relates to representativeness. Since participation in the registry is voluntary, the pregnant individuals who voluntarily enroll in the registry may not be representative of the overall population of pregnant individuals. This could introduce selection bias and affect the generalizability of the results. To minimize the potential for selection bias, a multi-faceted awareness strategy will be employed.

Because the registry will enroll individuals only after recognition of pregnancy and in some cases much later during pregnancy, there will be left truncation of the enrolled population. That is, the enrolled population of pregnant individuals will include individuals with a shortened period at risk of the outcomes and exclude individuals who have already had certain outcomes (e.g., SAB, induced abortion).

Additionally, individuals in the tirzepatide cohort may differ from those in the unexposed cohorts in important factors that could impact pregnancy outcomes (e.g., access to healthcare and medications, socioeconomic status, disease severity, etc.). To partly address this concern, this study includes two comparator cohorts, an AOM active comparator cohort, and an AOM

unexposed comparator cohort that has obesity or overweight with comorbidities at the time of conception.

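### SAB is analysed as a proportion with no entry time despite admitted left truncation; adjustment for gestational age at enrollment is optional, and the texts on method and exposure window conflict

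*Protocol*

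**What the plan says.** **Estimate.** Protocol Table 9.7 (Section 9.11.2.2) sets the SAB numerator as "SABs among individuals with pregnancy outcome data who are enrolled (and exposed, if applicable) prior to 20 gestational weeks". The denominator is everyone meeting the same conditions. Section 9.11.2.2 then gives a crude RR and an IPTW-weighted log-binomial RR.

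**Limitation.** Section 9.13 states that "there will be left truncation of the enrolled population", with a shorter time at risk for some and early losses missing. 

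**Method.** Section 9.11.2 says "All outcomes will be analyzed as binary variables". Section 9.11.2.2 says of SAB and preterm birth that "for these time-to-event outcomes, data will be censored at appropriate time points: 20 gestational weeks for SAB", and 37 weeks for preterm birth.

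**Exposure window.** Table 9.7 opens the SAB window at the date of conception (DOC): "SAB [Exposure: DOC to" 19 6/7 weeks. The preterm birth window also opens at DOC. Section 9.7.5 says "Individuals will be considered exposed during pregnancy if the exposure occurs any time from 25 days prior to the DOC to the pregnancy outcome". Section 9.7.1 and footnote b of Table 9.1 likewise reach back five half-lives.

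**Covariates.** Section 9.7.4 names gestational age at registry enrollment among variables that can be used. Section 9.11.2.4 leaves the forced propensity-score (PS) covariates to the SAP and adds covariates that stay imbalanced to the PS or outcome model.

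**The concern.** SAB risk is used up as gestation advances. Someone enrolling at week 18 has only two weeks of risk left before week 20, yet counts in the denominator exactly like someone enrolling at week 6. The proportion therefore mixes the SAB risk with the enrollment pattern. If the cohorts enter at different gestational ages, the crude RR can differ from 1 without any drug effect, or a real effect can be hidden. Even with identical entry patterns, the prevalence in each cohort falls short of the risk from early pregnancy, and Section 9.11.2 sets registry prevalences beside literature figures.

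The two conflicts affect who is counted and how. Censoring has no function in a proportion restricted to people with known outcomes. Someone whose only dose fell in the 25 days before DOC belongs to the tirzepatide cohort by one rule and lies outside the SAB window by the other.

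**Working it through.** **1. The plan's own SAB figures.** Table 9.4 uses 11.8% in the comparator, and Section 9.9.1 is "assuming a power of 80%, a 2-sided α level of 0.05, an equal number of individuals in each cohort". The Walters approximation with continuity correction requires the smallest n with

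n ≥ (1.960 + 0.842)² / {2[arcsin√(p1 − 1/(2n)) − arcsin√(p0 + 1/(2n))]²}.

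At RR 3, p0 = 0.118 and p1 = 0.354. With n = 57 the bracket is 0.6280 − 0.3640 = 0.2640 and the right side is 56.3, so 57 suffices. With n = 56 it is 56.5, so 56 does not. Over RR 1.5 to 5.5 the same formula gives "596 177 90 57 40 30 24 19 16", exactly as printed. The sample-size arithmetic is not in dispute.

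**2. Illustration with mixed entry, no drug effect (crude RR).** Assumed weekly SAB hazards: 2.0% in weeks 5–7, 1.0% in weeks 8–11, 0.15% in weeks 12–19. Cumulative risk is 1 − 0.98³ × 0.99⁴ × 0.9985⁸ = 10.7%. The risk left at entry is one minus the product over the remaining weeks:

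| Entry week | 6 | 8 | 10 | 12 | 14 | 16 | Mean entry |
|---|---|---|---|---|---|---|---|
| Risk left | 8.85% | 5.09% | 3.16% | 1.19% | 0.90% | 0.60% | |
| Cohort A mix | 25% | 25% | 20% | 15% | 10% | 5% | 9.5 |
| Cohort B mix | 10% | 15% | 20% | 20% | 20% | 15% | 11.4 |

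Weighting the risks by the mixes gives 4.41% and 2.79%. The spurious RR is 4.41/2.79 = 1.58.

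**3. Range over hazard shapes, fixed entry weeks (crude RR).** Spread H = −ln(1 − 0.118) = 0.1256 over weeks 5–19, either flat or falling by 14% or 26% a week. Risk from entry week e is 1 − exp(−hazard remaining). For the flat shape, week 8 gives 1 − exp(−0.1256 × 12/15) = 9.56% and week 12 gives 1 − exp(−0.1256 × 8/15) = 6.48%. The last column takes a true hazard ratio of 2, with tirzepatide entering at week 12 and the comparator at week 8.

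| Hazard | Risk from wk 8 | Risk from wk 12 | Null RR, 8 vs 12 | Null RR, 10 vs 12 | RR when true HR = 2 |
|---|---|---|---|---|---|
| Flat | 9.56% | 6.48% | 1.48 | 1.24 | 1.31 |
| −14%/week | 7.20% | 3.37% | 2.13 | 1.49 | 0.92 |
| −26%/week | 4.90% | 1.40% | 3.49 | 1.89 | 0.57 |

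With 364 × 0.9 ≈ 328 per cohort, an unadjusted two-proportion test at 0.05 rejects the true null for week 8 versus 12 in 31%, 59% and 73% of cases. The 328 is an upper bound, since Table 9.7 also requires enrollment before 20 weeks.

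**4. Effect of adjustment.** Simulation of 400,000 per cohort, entry SD 2.5 weeks, with stabilized weights on entry week truncated at the 1st and 99th percentiles as in Section 9.11.2.4. Ranges are over the three hazard shapes.

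| Mean entry (tirzepatide vs comparator), truth | Crude RR | IPTW RR, entry week in PS | Delayed-entry rate ratio |
|---|---|---|---|
| 8 vs 12, null | 1.48–3.02 | 1.08–1.18 | 0.99–1.01 |
| 10 vs 12, null | 1.24–1.85 | 1.00–1.06 | 0.99–1.02 |
| 12 vs 8, HR 2 | 0.64–1.32 | 1.65–1.80 | 1.98–2.00 |

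The null residual in the IPTW column comes mainly from the truncation rule acting where the entry distributions barely overlap; rerun without truncation, the null RR returns to about 1. In the last row, a small part of the gap from 2 is only that a risk ratio lies below the hazard ratio: with comparator risk r it equals 2 − r.

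**The case against.** The protocol does plan an adjusted RR. Gestational age at enrollment is a listed candidate. A covariate that is inspected and stays imbalanced is to be added to the PS model, and one with a standardized difference above 10% after weighting goes into the outcome model. Forced covariates are properly left to the SAP. Section 9.11.2.7 also contrasts those enrolling before and after prenatal testing, which partly tracks entry time. SAB is secondary with nominal p-values, and the truncation is disclosed.

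Much of this stands. The adjusted RR may end up nearly free of the problem, and the figures in steps 2 and 3 are crude. What does not stand is that the protocol secures this: the list in Section 9.7.4 is permissive, the prenatal-testing contrast does not compare cohorts on a gestational time scale, and weighting between cohorts does not restore the early losses missing from the absolute prevalence.

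The Table 9.7 bracket might be shorthand, with the general five-half-life rule carried over. The cell text, which asks only for exposure before 20 weeks, allows that reading, but the bracket does not state it.

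A reader might also infer more than the documents support:
- **That the cohorts will enter at different gestational ages.** Section 9.6.3.1 recruits tirzepatide users first, but tailors the comparator campaign for comparability. Different entry is possible, not shown.
- **That immortal time is material.** Section 9.7.1 does move a comparator participant who later becomes exposed into the tirzepatide cohort. Nothing indicates how many, and Section 7.4.3 says patients are advised to stop tirzepatide once pregnancy is recognized.
- **That preterm birth is biased to the same degree.** The calculations here concern SAB only.

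**Conclusion.** The point holds in this form. As written, SAB prevalence and the crude RR depend on enrollment timing, and protection of the adjusted RR is optional. The direction follows from the text. The size rests on hazards and entry weeks that the documents do not give: on the assumptions shown, a null crude RR of about 1.6 for a 1.9-week gap in mean entry and 1.5 to 3.5 for a four-week gap, falling to about 1.1 to 1.2 for the four-week gap if entry week is in the PS. It would be wrong to conclude that the planned adjusted RR is biased by these crude amounts, or that the protocol has no route to adjustment.

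The conflicts between time-to-event and binary, and between the two exposure windows, need no assumption. Both apply to SAB and to preterm birth.

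**What to change.** **SAB.** Specify an IPT-weighted time-to-event analysis on gestational age. Entry is at enrollment, or at first qualifying exposure if later. Censor at 20 weeks and treat induced abortion as a competing event. Report the delayed-entry cumulative incidence as the prevalence. Keep the proportion and RR as a sensitivity analysis, with gestational age at enrollment mandatory in the PS.

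**Preterm birth.** State one method, binary or time-to-event, in both Section 9.11.2 and Section 9.11.2.2.

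**Windows.** Reconcile the Table 9.7 exposure windows for SAB and preterm birth with Table 9.1 footnote b and Sections 9.7.1 and 9.7.5.

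**Cost.** Wording and programming only: consent date, EDD, exposure dates and outcome date are already collected (Section 9.8). A hazard ratio or cumulative-incidence ratio replaces the simple RR as the lead SAB estimate, while the Table 9.4 sizes are stated for an RR. Few individuals will be at risk in the earliest weeks, so the report must state the week from which cumulative incidence is counted.

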Hyperemesis gravidarum	Uncontrolled vomiting requiring hospitalization, severe dehydration, muscle wasting, electrolyte imbalance, ketonuria, and weight loss of more than 5% of body weight ⁵⁷	As reported by HCP.
Inadequate gestational weight gain	Gestation weight gain that is below the recommended range at term based on pregnancy weight category	The registry will use the 2009 gestational weight gain guidelines of the Institute of Medicine ⁵⁸ to determine inadequate maternal weight gain at term per maternal pre-pregnancy BMI category in singleton and twin gestations.
Spontaneous abortion (SAB)	An involuntary fetal loss or the expulsion of the products of conception occurring at <20 gestational weeks	Section 9.7.5 provides information on the methods used to calculate gestational age.
Stillbirth	As defined by the ACOG, an involuntary fetal loss occurring at ≥ 20 gestational weeks or, if gestational age is unknown, a fetus weighing ≥ 350 g ⁵⁹	Section 9.7.5 provides information on the methods used to calculate gestational age.
Induced abortion	An intervention that is intended to terminate a suspected or known ongoing intrauterine pregnancy and that does not result in a live birth ⁶⁰	As reported by HCP.
Preterm birth	A live birth occurring at <37 gestational weeks	Section 9.7.5 provides information on the methods used to calculate gestational age.

Outcome	Clinical Definition	Operational definition
Small for gestational age (SGA)	Birth weight <10th percentile for sex and gestational age using standard growth charts for full and preterm live-born infants ⁶¹	For the determination of SGA, the registry will utilize the sex-specific international growth reference standards from the INTERGROWTH-21st for those born between 24 ^{0/7} and 42 ^{6/7} gestational weeks. ^{62,63} The INTERGROWTH-21st standards are the latest available global reference standards, representing contemporary information from an international, multi-ethnic, diverse population, and have been specifically developed for modern research.

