9.11.1.3. Prospectively Enrolled Versus Retrospectively Enrolled Participants

The registry will encourage prospective registration; however, retrospective enrollment in the registry will be permitted. A prospectively enrolled participant is defined as a pregnant individual who enrolls or makes initial contact with the registry prior to pregnancy outcome. A retrospectively enrolled participant is defined as a pregnant individual who enrolls or makes initial contact with the registry after the pregnancy outcome (e.g., live birth, stillbirth, SAB, induced abortion) has occurred (up to 12-months after pregnancy outcome).

Retrospectively enrolled participants can introduce bias toward the reporting of more unusual and severe outcomes and are less likely to be representative of the general population than prospectively enrolled participants. Therefore, retrospectively enrolled participants will be excluded from the main analysis population but will be included in supplementary analyses.

Diagnostic prenatal tests (e.g., ultrasound to scan for structural defects at approximately 20 gestational weeks, chorionic villus sampling, and amniocentesis) can determine with high accuracy whether a fetus has a structural or chromosomal abnormality. Therefore, inclusion of individuals who have had diagnostic prenatal testing in the analysis population may introduce bias. To examine this potential bias, a sensitivity analysis that applies a stricter definition of prospective enrollment will be conducted. For this analysis, individuals who enroll or make initial contact with the registry prior to diagnostic prenatal testing (and pregnancy outcome) will be considered prospectively enrolled, and individuals who enroll or make initial contact with the registry after diagnostic prenatal testing, regardless of the results, will be considered retrospectively enrolled in addition to individuals who enroll after pregnancy outcome. In this sensitivity analysis, the outcomes of individuals who enroll prior to diagnostic prenatal testing will be compared with those of individuals who enrolled after diagnostic prenatal testing.

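### Table 9.7 counts late enrollees in the induced abortion denominator, so the prevalence is diluted and the crude risk ratio depends on when each cohort enrolls

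*Protocol*

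**What the plan says.** Protocol section 9.11.2.2, Table 9.7, sets the main induced abortion row as "Individuals with pregnancy ending in induced abortions" over "Individuals included in the analysis population", with exposure in any trimester. The sensitivity row uses "Induced abortions among individuals with pregnancy outcome data" over individuals with outcome data. Neither row mentions week of enrollment.

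Entry to the analysis population has no upper gestational week: "A prospectively enrolled participant is defined as a pregnant individual who enrolls or makes initial contact with the registry prior to pregnancy outcome".

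For spontaneous abortion (SAB), the row directly above, the denominator is "individuals with pregnancy outcome data who are enrolled (and exposed, if applicable) prior to 20 gestational weeks". The text after the table repeats this for SAB and preterm birth only: "prevalence will be calculated among the subset of individuals who are enrolled in the registry prior to 20 and 37 gestational weeks".

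Section 9.13 acknowledges left truncation. It says that some individuals will join well into pregnancy, and that the enrolled population will "exclude individuals who have already had certain outcomes (e.g., SAB, induced abortion").

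Section 9.7.3 defines induced abortion with no gestational limit: "An intervention that is intended to terminate a suspected or known ongoing intrauterine pregnancy and that does not result in a live birth".

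**The concern.** A woman who first contacts the registry late in an ongoing pregnancy has already passed the weeks in which she could have had, and been counted for, an earlier induced abortion. She can add little or nothing to the numerator but counts fully in the denominator. The reported proportion then mixes two things: the risk among those observed while at risk, and the share of the cohort that enrolled early enough.

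Prevalence is diluted even if all cohorts enroll at the same time. The crude risk ratio, which section 9.11.2.2 plans for all outcomes, is distorted only if timing differs between cohorts. The distortion can then suggest a difference that does not exist or hide one that does.

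Women who enroll after their own induced abortion are not the issue. They are retrospective enrollees and are already outside the main analysis population.

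**Working it through.** **The plan's own figures.** Table 9.4 gives 31 per cohort for induced abortion at a risk ratio of 3.0, with reference prevalence 18.6%, 80% power and two-sided 0.05. The Walters approximation is power = Φ(√(2n)·[asin√(p2 − 1/(2n)) − asin√(p1 + 1/(2n))] − 1.96). With p1 = 0.186 and p2 = 0.558, the smallest n reaching 80% is 31. All eight induced abortion cells reproduce (343, 100, 50, 31, 21, 15, 12, 9). Enrollment also reproduces: 265/0.9³ = 363.5, so 364 per cohort. After the assumed 10% exclusion, 364 × 0.9 ≈ 328 remain. The stated figures are sound; the problem lies in the denominator.

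**Inputs for the check.**
- s = share of a cohort enrolled while an induced abortion could still be observed. The protocol gives no enrollment-week distribution, so s is assumed, over 0.5 to 0.9.
- r = risk among those enrolled in time. 18.6% is used for illustration, with 5% as a lower case. The 18.6% has live births as its denominator in Table 9.4, so it is not on the Table 9.7 scale (0.186/1.186 = 15.7% of live births plus induced abortions).
- Risk after late entry is first taken as negligible.

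**Prevalence.** Reported prevalence = r × s. At r = 18.6%, s = 0.9 gives 16.7% and s = 0.5 gives 9.3%.

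**Crude risk ratio with no true effect.** Crude RR = (r·s_T)/(r·s_C) = s_T/s_C, where T is tirzepatide and C the comparator.

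| s_T | s_C | Crude RR |
|---|---|---|
| 0.9 | 0.9 | 1.00 |
| 0.9 | 0.7 | 1.29 |
| 0.8 | 0.5 | 1.60 |
| 0.9 | 0.5 | 1.80 |
| 0.7 | 0.9 | 0.78 |
| 0.5 | 0.8 | 0.62 |

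The mirror image of the 1.80 row would be 0.5/0.9 = 0.56. A true ratio of 1.5 with shares 0.5 and 0.8 would read 1.5 × 0.5/0.8 = 0.94.

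**Some risk after late entry.** If late enrollees carry a fraction k of the early risk, RR = [s_T + k(1 − s_T)]/[s_C + k(1 − s_C)]. For shares 0.8 and 0.5:
- k = 0.10 gives 0.82/0.55 = 1.49.
- k = 0.25 gives 0.85/0.625 = 1.36.

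**Chance of nominal p < 0.05 with no true effect** (Wald test on log RR, 328 per cohort):
- 0.9 against 0.7: 27% at r = 18.6%, 10% at r = 5%.
- 0.9 against 0.5: 79% at r = 18.6%, 28% at r = 5%.
- Equal shares: 5%.

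**Whether another planned analysis repairs this.**
- The sensitivity row adds only a requirement for outcome data, which the main population already largely imposes by excluding those lost to follow-up. It does not test enrollment timing.
- The stricter prospective-enrollment analysis (section 9.11.2.7) compares those enrolled before and after diagnostic prenatal testing. It shows results by early and late entry but does not change this denominator.
- Gestational age at enrollment is listed in section 9.7.4 among variables that may be considered. It can help the adjusted ratio, but not the crude ratio or the unadjusted prevalence.

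**The case against.** Several points on the other side stand and limit the finding.

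- A reader might infer that the table contradicts itself because SAB and preterm birth have enrollment limits and induced abortion does not. The documents do not support this. SAB ends by definition at 20 weeks and preterm birth at 37, so later enrollees cannot have those events. Induced abortion has no defined limit, so those rows are a useful analogy and no more.
- A reader might infer that comparators will enroll later in pregnancy, which would push the ratio above 1. Section 9.6.3.1 says only that the comparator campaign will be tailored once some tirzepatide participants have been characterised, in order to make the cohorts more alike. That is an order in calendar time, not in gestational age. The direction is unknown, and equal timing is possible.
- A reader might infer that the adjusted ratio shares the bias. Section 9.11.2.4 inspects variables outside the prespecified set for balance, adds those still imbalanced to the propensity score model, and puts any with a standardized difference above 10% after weighting into the regression. Late shares of 20% and 50% differ by 0.30/√((0.16 + 0.25)/2) = 0.66 standard deviations before weighting, so the variable would be picked up if it is among those inspected.
- A 20-week cut-off has a cost. The structural scan falls at about 20 weeks, and a prenatal finding is a recorded reason for induced abortion. Terminations among women enrolling after that scan may matter for safety and should not disappear from the analysis.
- A cut-off does not remove left truncation. Women entering at weeks 7 and 18 would still count equally.
- The limitation is disclosed in section 9.13, which promises descriptive evaluation of each source of bias.

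None of this changes the fact that the stated denominator makes the prevalence and the crude ratio depend on enrollment timing.

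**Conclusion.** The point holds for the prevalence and the crude risk ratio of induced abortion. Dilution of the prevalence needs only that some participants enroll late with reduced remaining risk, and section 9.13 expects late enrollment. Distortion of the crude ratio also needs timing to differ between cohorts, which is plausible but not established.

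The range of 0.62 to 1.80 rests on assumed shares of 0.5 to 0.9, equal true risk and negligible risk after late entry. It includes 1.00 and narrows if late enrollees keep some risk. The restricted ratio returns to 1.00 only if risk does not vary with entry week below the cut-off.

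The adjusted ratio is protected to the extent that gestational age at enrollment is balanced. Induced abortion is a secondary outcome with nominal p-values. The primary analysis of major congenital malformations and the target of 364 per cohort are unaffected.

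**What to change.** In Table 9.7, make the main induced abortion row individuals with pregnancy outcome data who enrolled (and, if applicable, were exposed) before a stated gestational week, for example 20 weeks as in the SAB row. Count their induced abortions at any later week, so that a woman enrolled at 10 weeks whose pregnancy is terminated at 22 weeks remains a case. Add the rule to the list of denominator restrictions below the table.

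Keep the current all-enrollee denominator as the sensitivity row, so that terminations among later enrollees, including those after the scan at about 20 weeks, are still reported. State that the cut-off reduces but does not remove left truncation.

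The cost is table wording and a smaller main denominator. No new data are needed: consent date, estimated date of delivery, exposure dates and outcome date are already collected under section 9.8.
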